#### 6.1.2 Response rate

Antibody responder is defined as the study subject whose serum antibody titer is greater than the response threshold (see section 9.2.2 for definition) at any visit after baseline. Response rate will be calculated as the percent of the number of antibody responders versus the total number of subjects for each arm.

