4 ANALYSIS VARIABLES

4.1 Demographic and Baseline Characteristics

The baseline value is defined as the last available value before the first injection of study drug. The following demographic and baseline disease characteristics will be summarized by treatment, by study center and overall for the randomized and treated population.

Demographic characteristics are defined as follows:

- Age (in years) to be derived as: (date of informed consent - date of birth)/365.25
- Gender (male/female)
- Body weight (kg)
- Body Mass Index (BMI, kg/m²): weight in kg/(height in meters)²
- Race

Disease characteristics including:

- Disease duration (years): (date of informed consent– date of diagnosis)/365.25
- APOE genotype
- Baseline scores of ADAS-Cog total score, MMSE total score, ADCS-ADL total score, CDR/CDR-SB total score, NPI total score

Inflammatory markers including:

- CRP
- ESR
- TNF- α
- IL-6
- IL-8

Physical examination, medical history and concomitant disease, previous and concomitant medication, and HIS score will be described at baseline.

The baseline safety data of clinical chemistry and hematology, inflammatory markers and number of microhemorrhages in the brain will also be summarized.

4.2 **Immunogenicity Variables**

The level of anti-A β antibodies is one of the primary endpoints and is assessed at baseline (V1) and every following visit (V2 to V13). The one-sided 95% confidence interval (CI, right side) from all visits (V1 to V13) for subjects in Arm 3 (placebo group) will be calculated as the threshold of response. Antibody responders will be defined as the subjects with serum antibody titer > response threshold at any visit after baseline.

Response rate, treatment difference and its 90% CI will be calculated.

The AUC of anti-A β antibodies will be served as exploratory endpoint. AUC will be calculated by the sum of individual trapezoid area under the curve of level of A β antibodies. In case of missing titer values, last observation carry forward will be used for AUC calculation.

4.3 **Efficacy Variables**

Efficacy variables are evaluated as secondary endpoints in this study.

The change from baseline in cognitive, functional, and global assessments through the end of the study

- Cognition: ADAS-Cog
 - The ADAS-cog 13 contains 13 items, with a total scoring range of 0 – 85 and higher scores indicating greater dysfunction.
- Cognition: MMSE

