5 STATISTICAL METHODS

5.1 General

Continuous data will be summarized by treatment group using the number of observations available (n), mean, standard deviation (SD), median, interquartile range (IQR), minimum, and maximum.

Categorical data will be summarized by treatment group using count and percentage. Missing data will not be categorized in the summaries.

In general, descriptive statistics of quantitative efficacy and safety parameters (results and changes from baseline) by scheduled visit will be provided on observed cases, i.e. the inclusion of only subjects with non-missing assessments at a specific visit.

For undetected value, this study will take the minimum value that can be detected as the text value, eg, <3.5 will be treated as 3.5 and <0.012 will be treated as 0.012 when performing the summary and will list the original value in listing.

- The pre-treatment period is defined as the time from the date of the informed consent to the time before the administration of first dose of study medication.
- The post-treatment period is defined as the time from after the first dose of study medication to the end of the study.

All statistical tests will be two-sided at the alpha level of 0.05, unless otherwise specified.

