5.9 Analysis of Immunogenicity Variable

Anti-A β antibodies will be summarized by presenting summary statistics of raw data and change from baseline values (n, mean, standard deviation, median, range) at each scheduled visit in mITT Population and PP Population.

The Kruskal-Wallis test or analysis of variance (ANOVA) for continuous variables for baseline information will be performed for comparing the un-adjusted change among Arm 1, Arm 2 and Arm 3.

A repeated-measures mixed-effects model with treatment (Arm 1+ Arm 2 vs. Arm 3, Arm 1 vs. Arm 3 and, Arm 2 vs. Arm 3), study visit, time-by-treatment, APOE4 status, and baseline as a

covariate will be used to analyze change from baseline of anti-A β antibodies. The unstructured covariance will be used in the modelling of the within-patient errors in the analysis. For APOE4 status subgroup analysis of MMRM, APOE4 factor will not be considered in the model. AUC of Anti-A β antibodies will be used an analysis of covariance (ANCOVA) model with treatment and baseline of Anti-A β antibodies as covariate. Antibody responders will be defined as the subjects with serum antibody titer > response threshold at any visit after baseline. The number and percentage of patients will be tabulated for each treatment group in mITT Population and PP Population at each post treatment scheduled visit. Treatment differences in the proportion antibody responders will be analyzed with the Chisq test. The one-sided 95% confidence interval (CI, right side) from all visits (V1 to V13) for subjects in Arm 3 (placebo group) will be calculated as the threshold of response.

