5.10 Analysis of Efficacy Data

Efficacy analyses will be performed on the mITT and PP populations. For change from baseline of ADAS-Cog total score, MMSE total score, ADCS-ADL total score, CDR-SB total score, NPI total score, A repeated-measures mixed-effects model with treatment (Arm 1 + Arm 2 vs. Arm 3, Arm 1 vs. Arm 3 and , Arm 2 vs. Arm 3), study visit, time-by-treatment, APOE4 status, and baseline as a covariate will be used to analyze change from baseline. The least square means using maximum likelihood estimate and its 95% will be provided. The unstructured covariance will be used in the modeling of the within-patient errors in the analysis.

For change from baseline of mean SUVR, A repeated- measures mixed-effects model with treatment (Arm 1 + Arm 2 vs. Arm 3, Arm 1 vs. Arm 3 and, Arm 2 vs. Arm 3), study visit, time-by-treatment, APOE4 status, and baseline as a covariate will be used to analyze change from baseline. The unstructured covariance will be used in the modeling of the within-patient errors in the analysis.

For change from baseline of mean SUVR by region, A repeated- measures mixed-effects model with treatment (Arm 1 + Arm 2 vs. Arm 3, Arm 1 vs. Arm 3 and, Arm 2 vs. Arm 3), study visit, time-by-treatment, and baseline as a covariate will be used to analyze change from baseline. The unstructured covariance will be used in the modeling of the within-patient errors in the analysis.

The p-values and confidence intervals for these efficacy endpoints were not adjusted for multiplicity, it should be used for screening purposes only, and that one side of 95% confidence intervals are provided to help gauge the precision of the estimates for treatment difference.

The proportion of PET positive subjects with visual read will be provided by number and percentage for each treatment group in mITT Population and PP Population at each post treatment scheduled visit. Treatment differences will be analysed with the Chisq test. The one-sided 95% confidence interval (CI, right side) between (Arm 1 + Arm 2 vs. Arm 3, Arm 1 vs. Arm 3 and, Arm 2 vs. Arm 3) from all visits will be calculated.

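### The antibody-responder cut-off is a one-sided 95% confidence limit of an unnamed parameter of pooled placebo titers; read in its ordinary sense, it does not separate responders from non-responders

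*SAP*

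**What the plan says.** Protocol 3.2.1 and SAP 2.3 list response rate among the primary immunogenicity measures. Protocol 6.1.2 makes it depend on a threshold: "Antibody responder is defined as the study subject whose serum antibody titer is greater than the response threshold". Protocol 9.2.2, SAP 4.2 and SAP 5.9 define that threshold in the same words: "The one-sided 95% confidence interval (CI, right side) from all visits (V1 to V13) for subjects in Arm 3 (placebo group) will be calculated". None of the three says what the interval is for, whether titers are on a raw or log scale, or how up to 13 titers from one subject enter the calculation.

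The responder rule is: "Antibody responders will be defined as the subjects with serum antibody titer > response threshold at any visit after baseline". Titers are taken at V1 to V13, so there are 12 chances to qualify, with no confirmation and no required rise over baseline.

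On reporting, SAP 4.2 adds "Response rate, treatment difference and its 90% CI will be calculated". SAP 5.9 says the responder counts "will be tabulated for each treatment group in mITT Population and PP Population at each post treatment scheduled visit", and "Treatment differences in the proportion antibody responders will be analyzed with the Chisq test". Neither section names the arms in the responder contrast. SAP 5.9 does not say whether the test uses the any-visit or a by-visit status.

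On undetected values, SAP 5.1 states: "For undetected value, this study will take the minimum value that can be detected as the text value".

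**The concern.** A confidence limit ordinarily describes an estimated parameter, most often a mean. SAP 5.10 uses the same phrase in that sense, for a between-arm comparison: "The one-sided 95% confidence interval (CI, right side) between (Arm 1 + Arm 2 vs. Arm 3". Protocol section 1 reports that the Phase I cut-off was a one-sided upper limit placed on the average titer at baseline. On that reading the limit closes in on the mean as values accumulate and says nothing about the spread of individual titers. A subject with no vaccine response would then usually exceed it at some visit.

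A responder threshold is nevertheless applied to individual titers, so an individual 95% limit is also a plausible intention. The text does not decide between the two. Two analysts could follow it faithfully and report very different primary response rates from the same data. If the parameter stays unnamed, the choice could also be made after database lock.

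**Working it through.** The documents state no expected placebo response rate or power for this endpoint, so there is no figure of the plan to reproduce first.

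**Inputs from the documents.** 15 placebo subjects (SAP 5.13); 13 titer visits, 12 of them after baseline (SAP 4.2); a strict greater-than rule (SAP 4.2); undetected values set to the detection minimum and a two-sided alpha of 0.05 (SAP 5.1).

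**Assumptions.** The documents give no placebo titer distribution, within-subject correlation or share of values at the floor. Assumed here: complete data, no vaccine effect or drift in Arm 3, normal titers (for example log titers), and correlation 0 to 0.9.

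**Step 1: position of the two cut-offs.** Pooled values: 15 × 13 = 195.
- Limit of the mean, treating values as independent: t(0.95, 194)/√195 = 0.118 SD above the mean. Share of placebo titers above it at one visit: 1 − Φ(0.118) = 45%.
- Individual limit, mean + 1.645 SD: 5% at one visit.

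**Step 2: any of 12 visits, independent titers.**
- Limit of the mean: 1 − (1 − 0.453)^12 = 99.9%.
- Individual limit: 1 − 0.95^12 = 46.0%.

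**Step 3: correlated titers.** Simulation of 15 subjects × 13 visits, 4,000 replicates, with the cut-off computed from the 195 simulated values each time. Placebo subjects counted as responders:

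| Correlation | Limit of the mean | Individual limit |
|---|---|---|
| 0 | 99.9% | 46% |
| 0.3 | 96% | 36% |
| 0.5 | 91% | 29% |
| 0.7 | 82% | 22% |
| 0.9 | 67% | 14% |

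At correlation 0.99 the rates are 52% and 7%. Log-normal titers analysed on the raw scale (ln-SD 0.7) give 54% to 99% and 19% to 55% over correlation 0.9 to 0. Handling of repeats matters too: basing the limit of the mean on 15 subject means lowers the normal-titer figure at correlation 0.9 from 67% to 54%.

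**Step 4: detection floor** (normal or log-normal, correlation 0 to 0.9).

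| Placebo titers at the floor | Limit of the mean | Individual limit |
|---|---|---|
| 80% | 27% to 88% | 15% to 61% |
| 95% | 11% to 44% | 9% to 43% |
| 99% | 3% to 11% | 3% to 11% |
| 100% | 0% | 0% |

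The last row is 0% because a titer equal to the floor does not exceed a threshold equal to the floor.

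**Step 5: effect on the contrast.** Exact power of the uncorrected chi-square test, assuming 100% active response. SAP 5.9 names no responder contrast, so both group sizes are assumptions.

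| Placebo rate | 15 v 15 | 30 v 15 |
|---|---|---|
| 90% | 6% | 45% |
| 80% | 35% | 83% |
| 66% | 81% | 98% |
| 46% | 99% | 100% |

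**Step 6: where the cut-off should come from.** At correlation 0.5 without drift, mean + 1.645 SD gives an any-visit placebo rate of 29% from pooled Arm 3 titers and 28% from the pre-dose V1 titers of all 45 subjects. With an assumed linear drift of 1 SD by Week 78 (correlation 0 to 0.9), the Arm 3 source gives 18% to 49% any-visit and 12% to 13% at Week 78. The V1 source gives about 33% to 81% and about 27%. The improvement therefore comes from naming an individual limit, not from changing the source.

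**The case against.** The strongest reply is that the size of the problem is assumed. If nearly all placebo titers are undetectable, which the documents neither state nor exclude, the two readings converge and the inflation is small or nil. The trial is exploratory, SAP 5.15 keeps p-values for screening, by-visit rates without any-visit compounding are already planned, and the change-from-baseline titer analysis does not use the cut-off. All of this stands and limits the severity. It does not supply the missing definition of a primary measure whose rates will be reported whatever role the p-values have.

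A reader might infer three stronger things that the documents do not support.
- *That the formula can be settled only after unblinding, because the cut-off uses Arm 3 titers.* Only the numerical value needs Arm 3 codes. The formula can be written at any time before lock, and the blinding of analysts until lock in Protocol 6.4 is no obstacle.
- *That the error is simply conservative.* A low cut-off shrinks the difference between active and placebo, but it also makes it easier for active subjects to qualify. Each arm's rate is reported (Protocol 9.4.3, SAP 5.9), and for those stand-alone active rates the error is favourable.
- *That the threshold must move to pre-dose samples.* Concurrent placebo titers partly absorb assay or vehicle drift, and the V1 source does worse when there is drift.

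**Conclusion.** The point holds and should be fixed. The threshold of a primary measure is a confidence limit with no named parameter or scale. In its ordinary sense it sits about 0.12 SD above the placebo mean, which does not distinguish a response from background. With normal titers, no floor and correlation 0 to 0.9, the placebo response rate would be about 67% to 100% on that reading and about 14% to 46% under an individual limit.

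It would go too far to say that the placebo rate will be inflated or that the comparison will fail. Inflation depends on the reading, the correlation and the floor share. With 100% active response assumed, serious power loss needs a placebo rate of roughly 80% or more, which in these illustrations means the limit-of-the-mean reading with a substantial share of titers above the floor. The ambiguity itself depends on none of these assumptions.

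**What to change.** Before database lock, amend SAP 4.2 and 5.9, and either amend Protocol 9.2.2 or record the change in SAP section 6:

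1. Replace the confidence limit with a named upper 95% reference limit for individual titers, keeping the Arm 3 V1 to V13 source. One option is the log10 mean + 1.645 SD. Another is one named empirical 95th-percentile method, chosen in advance if many values at the floor are expected. State how repeated titers enter.
2. Keep the any-visit definition, state that its placebo rate is expected to exceed 5% (about 14% to 46% in the no-floor illustration), and report it beside the planned by-visit rates.
3. Add response at two consecutive visits as a prespecified sensitivity analysis. The simulated placebo rate is about 3% to 7% without drift or floor.
4. Name the arms compared, and the responder status used, in the chi-square test and the 90% CI.
5. If wanted, add a cut-off from the pre-dose V1 samples of all subjects as a sensitivity analysis, not as the replacement.

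The cost is one derivation and a text change, with no new samples. There are three downsides to state. A higher cut-off may lower the active rates. The result will not be comparable with the 100% reported for Phase I. The two-visit rule loses transient responders and may bear differently on Arm 2, which receives placebo at Weeks 24 and 48.

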#### 6.1.1 Anti-A $\beta$ antibody measurement

For the immunogenicity assessment of the investigational product, UB-311, the level of anti-A $\beta$  antibodies in the serum samples will be measured by a validated enzyme immunoassay manufactured by United Biomedical, Inc. (UBI).

The level of anti-A $\beta$  antibodies is assessed at every visit throughout the study period from V1 to V13 (Weeks 0/baseline, 4, 12, 16, 24, 28, 36, 40, 48, 52, 60, 64, and 78). For visits that UB-311 or placebo is scheduled to be administrated (V1, V2, V3, V5, V7, V9, and V11), blood samples will be collected before the treatment.

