3 STUDY DESIGN

This is a 78-week, multicenter, randomized, double-blind, placebo-controlled Phase IIa study. Eligible subjects, 60 years or older with mild Alzheimer’s disease (AD), will be further screened by ¹⁸F-AV-45 PET scan for the presence of amyloid deposition.

Enrolled subjects will be randomized into one of the 3 treatment arms in 1:1:1 ratio. Subjects assigned to Arm 1 will receive 7 doses of UB-311 at Weeks 0, 4, 12, 24, 36, 48, and 60.

Subjects assigned to Arm 2 will receive 5 doses of UB-311 at Weeks 0, 4, 12, 36, and 60, and placebo at Weeks 24 and 48. Subjects assigned to Arm 3 will receive placebo at Weeks 0, 4, 12, 24, 36, 48, and 60. Subjects will be followed until Week 78. Subjects enrolled in the Phase I trial with UB-311 will be excluded from the Phase IIa trial.

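### Carrying the last titre forward in the exploratory antibody AUC treats a rising and waning titre as constant, and the resulting error falls on the two vaccine arms only

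*SAP*

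**What the plan says.** SAP 4.2 defines the AUC: "AUC will be calculated by the sum of individual trapezoid area under the curve of level of A"β antibodies. It then adds the missing-data rule: "In case of missing titer values, last observation carry forward will be used for AUC calculation". It does not separate an isolated missed visit from dropout, and it does not say whether titres enter on the raw or the log scale. The same section says the AUC "will be served as exploratory endpoint", which agrees with SAP 2.5.

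SAP 5.9 says the AUC "will be used an analysis of covariance (ANCOVA) model with treatment and baseline of" antibody level as covariate.

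Protocol 6.1.1 sets the titre samples at "Weeks 0/baseline, 4, 12, 16, 24, 28, 36, 40, 48, 52, 60, 64, and 78". At dosing visits "blood samples will be collected before the treatment". SAP 3 has Arm 1 "receive 7 doses of UB-311 at Weeks 0, 4, 12, 24, 36, 48, and 60"; Arm 2 has active doses at Weeks 0, 4, 12, 36 and 60, with placebo at Weeks 24 and 48. Protocol 5.2 explains the two booster frequencies as a way to learn what is needed to keep antibody levels up.

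SAP 5.2 contains no other rule for missing titres. The only sensitivity analyses announced in SAP 6 concern outliers.

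**The concern.** LOCF assumes that the titre stays where it was last seen. The design expects the opposite in Arms 1 and 2. Boosters are given because levels may fall. From Week 12 on, each injection visit gives a pre-dose sample and the next visit a sample 4 weeks after the injection. The last sample, at Week 78, comes 18 weeks after the final dose. The value carried forward therefore depends on where in the dosing cycle the subject was last seen, and it is held for up to the rest of the 78 weeks.

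A placebo titre with no vaccine-driven rise is the same whether carried or observed. The error is thus confined to the vaccine arms, and it differs between them because their active doses differ.

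The AUC is the only planned summary of cumulative antibody exposure, and comparing maintenance schedules is a stated purpose of the design. With 15 subjects per arm, one or two dropouts can matter. No planned sensitivity analysis would reveal the error.

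**Working it through.** The plan gives no AUC figure to reproduce. It also gives no titre values, half-life or dropout rate, so every size below rests on assumptions.

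**Inputs from the documents:** 13 sampling weeks (Protocol 6.1.1), active-dose weeks (SAP 3), 15 per arm (SAP 5.13), trapezoid rule and LOCF (SAP 4.2).

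**Assumed:** half-life h = 6, 12 or 24 weeks.

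**Step 1. One subject, last sample Week 16, no later injection.** Set the Week 16 titre to 1, so that afterwards the true titre is 2^(−(t−16)/h). LOCF gives 1 × (78 − 16) = 62. The area before Week 16 is assumed to be 5.6.

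| h (weeks) | True area, Weeks 16–78 | 62 / true | Weeks 0–78: 67.6 / (true + 5.6) |
|---|---|---|---|
| 6 | 9.17 | 6.8 | 67.6/14.77 = 4.6 |
| 12 | 17.09 | 3.6 | 67.6/22.69 = 3.0 |
| 24 | 28.98 | 2.1 | 67.6/34.58 = 2.0 |

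**Step 2. Arm mean with two such subjects of 15.** This needs completers' AUCs. Assumed: baseline 1; each dose adds a rise that peaks 4 weeks later (5, 40, then 100 units for doses 1, 2 and 3 onward) and decays with half-life h; rises add up. Shift = 2(L − T) / (13F + 2T), where L is the dropout's LOCF AUC, T the true AUC after stopping, and F a completer's AUC.

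| h | L | T | F, Arm 1 | Shift, Arm 1 | F, Arm 2 | Shift, Arm 2 |
|---|---|---|---|---|---|---|
| 6 | 7767 | 1580 | 5945 | 12374/80445 = 15.4% | 3731 | 12374/51663 = 24.0% |
| 12 | 8490 | 2756 | 9184 | 11468/124904 = 9.2% | 5737 | 11468/80093 = 14.3% |
| 24 | 9004 | 4536 | 13326 | 8936/182310 = 4.9% | 8424 | 8936/118584 = 7.5% |

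If each active dose instead returns the titre to the same peak, the shifts for h = 6, 12 and 24 are 16%, 12% and 8% (Arm 1) and 22%, 14% and 9% (Arm 2). The order of magnitude does not depend on this choice.

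**Step 3. Timing and direction** (Step 2 kinetics, Arm 1, h = 12, error in one subject's AUC).
- No injection after the last sample: +109% if the last sample is Week 24, +58% at Week 36, +28% at Week 48, +8% at Week 64.
- Dosing continues but titres are missing: −95% at Week 4, −72% at Week 12, −37% at Week 24 (pre-dose), +10% at Week 28 (post-dose), +12% at Week 52. In Arm 2 the same calculation gives +48% at Week 16, 0% at Week 24, −34% at Week 36 and +30% at Week 40.
- Flat placebo: 0% throughout.

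A subject who is sampled, injected the same day and then lost lies between these cases. With Week 4 as the last sample, the AUC is understated by 1%, 46% or 68% for h = 6, 12 or 24.

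**Step 4. Scale and single gaps.** On the log10 scale, the stopped-dosing error for a last sample at Week 24 (h = 12) is +34% instead of +109%. One isolated missed visit (raw scale, h = 12) changes the LOCF AUC by about −7% to +5% in Arm 1 and −14% to +5% in Arm 2. Linear interpolation does no better (−8% to +5% and −14% to +7%). Dropout is the problem, not single gaps.

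**The case against.** **Reach.** The AUC is exploratory. The primary change in antibody level is analysed by a repeated-measures mixed model with no LOCF stated, and responder status does not use the rule. This stands and limits the severity.

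**Missing data may be few.** Protocol 4.4 seeks an early termination visit with an antibody level and encourages withdrawn subjects to attend their remaining visits. This also stands, but it reduces missing titres without guaranteeing against them. The mITT definition (SAP 5.3.1) accepts a post-baseline value in any primary or secondary variable. A vaccinated subject with no post-baseline titre could therefore have the baseline value carried to Week 78.

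**Week 16 is an unfavourable case.** It is the first sample after the third dose and leaves a long tail. Step 3 shows the error shrinking with later dropout.

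**The mixed model is no cure for every target.** Its visit means in effect give dropouts the path of subjects still being dosed. For a subject who stopped after Week 16 (Arm 1, h = 12), the true AUC is 2756, LOCF gives 8490 and the completer path 9184. Against actual exposure after stopping, the model is no nearer than LOCF. This stands, and it is why the target must be stated.

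**Stronger readings a reader might infer.**
- *The arm mean is inflated by up to about half.* Multiplying the per-subject excess by 2/15 gives 2/15 × (4.6 − 1) = 48% down to 2/15 × (2.0 − 1) = 13%. That requires a 3-dose dropout to have a completer's true AUC, which the scenario excludes.
- *The rule can reverse the ranking of the two regimens.* Individual crossings occur: at h = 12 the Week 16 dropout's LOCF AUC exceeds an Arm 2 completer's (8490/5737 = 1.48). The arm means do not cross in this illustration. With two such dropouts in Arm 2 and none in Arm 1, Arm 2 averages (13 × 5737 + 2 × 8490)/15 = 6104 against 9184. SAP 5.9 also lists no Arm 1 versus Arm 2 contrast.
- *The rule could manufacture a vaccine response.* A vaccine with no effect would leave flat titres and no such error.

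**Conclusion.** The concern holds for the exploratory AUC. The stated rule rests on a constant titre, which the dosing rationale contradicts, and neither another titre rule nor a planned sensitivity analysis offsets it. The direction is not fixed: upward when no injection follows the last sample; either way when dosing continues unseen, depending on whether that sample was pre-dose or post-dose.

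The per-subject error can be two- to almost fivefold for early dropout. The arm-level error for two Week 16 dropouts in 15 is about 5–15% (Arm 1) or 7.5–24% (Arm 2). Both depend on assumed half-lives and raw-scale kinetics, and on a dropout count that the documents do not give. Later dropout, or a log scale, gives smaller errors. The documents do not support a claim that regimen rankings reverse or that any primary or secondary conclusion changes. This should be corrected before analysis, in proportion to an exploratory endpoint.

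**What to change.** In SAP 4.2 and 5.9:

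1. Remove LOCF from the main AUC analysis.
2. State whether the AUC targets antibody exposure under the regimen as scheduled, or actual exposure including the time after stopping, and state the titre scale.
3. For the as-scheduled target, obtain each AUC contrast as a trapezoid-weighted linear combination of the visit means from the mixed model already planned in SAP 5.9, on the same titre scale. Name a fallback covariance structure, because an unstructured matrix over 12 post-baseline visits has 12 × 13 / 2 = 78 parameters for 45 subjects.
4. Use titres collected after discontinuation, including the early termination sample, where available.
5. Keep AUC to the last observed titre divided by observed time as a sensitivity analysis only, since it still depends on when subjects drop out.

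The cost is a few SAP sentences and one added estimate statement, with no new data. The downside is that the model-based AUC assumes missing at random and does not estimate exposure after stopping. If that is the target, it must be estimated from post-discontinuation titres, which may be few.
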